Heart Failure Medication Study

Version: 6

Date: July 19, 2018

NCT Number: NCT03402750

1) Protocol Title

Heart Failure Medication Study

2) Objectives*

The objective of this investigation is to pilot test a medication in-hand intervention (Meds to Beds) compared to standard care for patients with heart failure (ICD-50[all numbers]). We expect the intervention to improve adherence and physical health, and reduce hospital re-admissions. We also expect the study to provide evidence for the feasibility and acceptability of the medication-in-hand intervention.

3) Background*

Heart failure is a chronic disease that increases mortality, reduces quality of life, and increases health care system costs. About 6.5 million people in the United States and 26 million worldwide have heart failure. Heart failure patients face many barriers to adherence to their medication regimen, including being prescribed an average of 6.4 medications daily. Promoting continuity of care in regard to prescription medication from the bedside with a medication in-hand intervention (Meds to Beds) may therefore help patients with heart failure improve adherence to medications, and thus improve health.

4) Inclusion and Exclusion Criteria*

Primary inclusion criterion is an admission diagnosis of heart failure ICD-50, including I50.1, I50.2, I50.20, I50.21, I50.22, I50.23, I50.3, I50.30, I50.31, I50.32, I50.33, I50.4, I50.40, I50.41, I50.42, I50.43, I50.8, I50.81, I50.810, I50.811, I50.812, I50.813, I50.814, I50.82, I50.83, I50.84, I50.89, I50.9, or any combination thereof.

To be included patients must also be:

1. age 18 or older;
2. in New York Heart Association Heart Failure Class II or Class III, with ejection fraction below 45%;
3. Cognitively intact, without significant psychological impairment affecting medication adherence such as dementia noted in patient record.

Exclusion criteria are:

1. Patients with medical conditions, such as active cancer or pregnancy, expected to alter heart failure medication management;
2. Patients discharged to nursing homes or hospice care, as they may not be responsible for their own adherence;
3. Prisoners and those unable to provide a point of contact for follow-up assessment;
4. Patients who do not plan to fill discharge medications at the Jackson Memorial Hospital pharmacy.

5) Procedures Involved*

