This study is expected to be of minimal risk to participants. Special care will be taken to ensure patients do not confuse participation in this study with their treatment plan, and continue to contact their regular providers for any issues or questions regarding their medication or health.

9) Potential Benefits to Subjects*

This study provides no direct benefit to participants.

10) Vulnerable Populations*

This study will not include pregnant women, prisoners, children or cognitively impaired adults.

11) Setting

Some study data will be collected at inpatient units at Jackson Memorial Hospital, with follow-up via telephone or in-person with these participants.

12) Resources Available

[name], BSN, RN, PhD is a fourth-year doctoral student in Nursing at the University of Miami School of Nursing and Health Studies. She has spent the past three years researching cardiovascular disease and medication adherence, including a participating in graduate-level nursing clinical at Jackson Memorial Hospital. She is fully bilingual in English and Spanish, and will be responsible for all data collection.

13) Prior Approvals

Approval of Jackson Memorial Hospital will be obtained before commencing this study.

14) Recruitment Methods

A partial HIPAA waiver will be requested to identify patients admitted to Jackson Memorial Hospital with a heart failure diagnosis who may qualify for the investigation. These patients will be approached at bedside by a known person such as a nurse or physician and invited to participate in the study. If interested in participating patients will be screened by researcher with a preliminary questionnaire regarding medical history and contact information. Qualifying patients will be asked to sign a consent form. At the time of inclusion in the study, participants will receive a gift card worth \$20 as compensation. In addition, participants will receive \$50 as compensation for completing the telephone follow-up portion of the study.

15) Local Number of Subjects

There will be up to 60 participants (30 Meds to Beds, 30 standard care).

16) Confidentiality

Patient confidentiality will be maintained at all times; they will only be contacted by one researcher. Data and responses will be linked using a numerical ID; a linking list with names matched to ID will be stored separately from data by the principal investigator in secure location.

IRB Study Number: HRP-503 20160741

Version #6 July 19, 2018

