Statistical Analysis Plan

Heart Failure Medication Adherence

Date: July 19, 2018

Version: 1

NCT Number: NCT03402750

Data Analysis Plan

Statistical Assumptions. It is necessary to confirm the assumptions of the statistical tests that will be used in this study (ANOVA, repeated measures ANOVA, and chi-square). For repeated measures ANOVA, the assumptions are multivariate normality (a normal distribution to higher dimensions), homogeneity of the covariance matrices (that these be similar across groups), and independence of the variables. Multivariate normality will be tested using Mardia's multivariate kurtosis (Yuan, Lambert & Fouladi, 2004). Homogeneity of the covariance matrices will be tested with Mauchly's sphericity test (Mauchly, 1940). There is no statistical test for independence, but the randomized design of the study supports this assumption. ANOVA has similar assumptions, which will also be tested. Chi-square will be used if assumptions are violated. For the chi-square test, the assumptions are that the data is categorical and that the groups are independent. These assumptions will be met as a result of the study design and appropriate sample size.

Hypotheses

Hypothesis 1. Participants in the intervention group will have better medication adherence than the control group.

Hypothesis 1A. Medication adherence (calculated with medication possession ratio) of participants in the intervention group will be higher than those in the control group at 30 days.

Hypothesis 1B. Self-reported medication adherence among participants in the intervention group will be higher than those in the control group at 30 days.

These hypotheses will be tested using ANOVA.

Hypothesis 2. The Meds to Bed intervention will have strong feasibility and acceptability.

Hypothesis 2A: The Meds to Beds intervention will have at least 90% successful deliveries of medication before discharge.

Hypothesis 2B: Participants in the Meds to Beds condition will report a better experience obtaining hospital discharge medications than those in the control group.

Hypothesis 2C: Participants in the Meds to Beds condition will report a better experience overall in the study than those in the control group.

Hypothesis 2A will be tested with a proportion in the intervention condition. Hypotheses 2B and 2C will be tested using ANOVA.

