Hypothesis 3. Participants in the intervention group will have lower deterioration in physical health from baseline to 30 days after discharge than the control group.

This hypothesis will be tested using repeated measures ANOVA.

Hypothesis 4. Participants in the intervention group will have a lower proportion of readmissions and deaths than the control group.

Hypothesis 4A. The intervention group will have a lower proportion of readmissions at 30 days than the control group.

Hypothesis 4B. The intervention group will have a lower proportion of deaths at 30 days than the control group.

These hypotheses will be tested using a chi-square test.

Hypothesis 5. Participants in the intervention group will have lower increases in mechanisms of action variables 30 days after discharge than the control group.

Hypothesis 5A. The average length of time (in 0-30 days) before beginning a prescription medication regimen for participants in the intervention group will be lower than among those in the control group.

Hypothesis 5B. Participants in the intervention group will report lower increases in Personal Inconvenience (*Patient Factor* of belief that medications will be difficult to obtain) than those in the control group.

Hypothesis 5C. Participants in the intervention group will report a higher score in in Immediacy of Benefit (*Therapy-related factor*) than those in the control group.

Hypothesis 5D. Participants in the intervention group will report lower increases in Fatigue (*Condition-related Factor*) than those in the control group.

Hypothesis 5E. Participants in the intervention group will report lower increases in Family Inconvenience (*Social/economic factor* of reduced family support) than those in the control group.

Hypothesis 5F. Participants in the intervention group will report lower increases in Prescription-related Paperwork (*Health care team / health system factor*) than those in the control group.

Hypotheses 5A-5F will be tested using ANOVA or repeated measures ANOVA, depending on the number of times the outcome is assessed.

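### Thirteen directional between-arm tests have no primary outcome, no error control, no exploratory label and no rule for when H1 is met; with no true effect, about 10–28% of such trials would show at least one favourable significant result

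*SAP*

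**What the plan says.** Section 2 of the protocol describes a pilot test and lists its expected effects without ranking them: "We expect the intervention to improve adherence and physical health, and reduce hospital re-admissions". Section 15 sets the size at up to 60 participants, 30 per arm.

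The SAP section on hypotheses assigns a test to each one:

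- H1: "Hypothesis 1. Participants in the intervention group will have better medication adherence than the control group". It has two parts, medication possession ratio (1A) and self-report (1B). "These hypotheses will be tested using ANOVA".
- H2: "Hypothesis 2A will be tested with a proportion in the intervention condition. Hypotheses 2B and 2C will be tested using ANOVA".
- H3 (physical health): "This hypothesis will be tested using repeated measures ANOVA".
- H4 (readmissions 4A, deaths 4B): "These hypotheses will be tested using a chi-square test".
- H5 (mechanisms): "Hypotheses 5A-5F will be tested using ANOVA or repeated measures ANOVA, depending on the number of times the outcome is assessed".

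Every between-arm hypothesis predicts a result in favour of the intervention. Neither document gives a significance level, sidedness, a primary outcome, a testing order or a multiplicity adjustment. Neither calls any test exploratory or says how many parts of H1, H2, H4 or H5 must succeed for the parent statement to hold.

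**The concern.** When many outcomes are tested and none is ranked, the result that gets emphasised can be chosen after the data are seen. H1 shows this most clearly. It is one statement about adherence resting on two measures that may disagree, so it could be claimed on whichever came out favourable. H2, H4 and H5 leave the same question open.

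At stake is how far a favourable p-value from this pilot can be trusted. A reader shown one significant difference cannot tell from the SAP whether it was the result the study was set up to find or the best of 13.

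**Working it through.** The documents contain no significance level, power or sample-size calculation, so there is no stated figure to reproduce.

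**Count of between-arm tests (from the SAP).** H1: 2. H2: 2 (2A is a proportion in one arm and is not counted). H3: 1. H4: 2. H5: 6. Total 2 + 2 + 1 + 2 + 6 = 13.

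**Assumptions, none stated in the documents.** Each test is run at 0.05 two-sided. With two groups, the ANOVA F-test and the chi-square test are non-directional, so two-sided is the natural reading. There is no true effect on any outcome. The correlation between outcomes is unknown, so a common value from 0 to 0.8 is shown.

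**Which event to count.** All 13 hypotheses favour the intervention, so only a significant result in that direction can support one. Under a two-sided 0.05 test its chance is 0.025 per test.

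**Independent outcomes.**

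- Favourable direction: 1 − 0.975^13 = 0.280.
- Either direction, or one-sided 5% tests: 1 − 0.95^13 = 0.487.

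**Correlated outcomes.** The first results column treats the test statistics as equally correlated normal variables. The other columns come from 40,000 simulated null trials with 30 per arm, 11 t-tests and 2 uncorrected chi-square tests, assuming a readmission rate of 20% and a death rate of 5%.

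| Correlation | Favourable, two-sided 0.05 (normal) | Favourable, two-sided 0.05 (simulated) | Favourable, one-sided 5% (simulated) | Either direction, two-sided 0.05 (simulated) |
|---|---|---|---|---|
| 0 | 28.0% | 27.4% | 48.7% | 47.9% |
| 0.3 | 21.4% | 21.6% | 37.2% | 42.1% |
| 0.5 | 16.7% | 17.5% | 30.2% | 34.8% |
| 0.7 | 12.0% | 13.4% | 23.9% | 26.7% |
| 0.8 | 9.6% | 10.9% | 20.1% | 22.1% |

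The two favourable, two-sided columns agree to within about 1.5 percentage points. The chi-square test for deaths is conservative when deaths are rare (two-sided size about 2.8% at a 5% death rate), which lowers the total only slightly.

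**H1 alone, favourable direction, independent parts.**

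- Either measure suffices: 1 − 0.975² = 0.0494. Positive correlation lowers this.
- Both measures required: 0.025² = 0.0006.

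**Other subsets, favourable direction, independent.**

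- H5 (6 tests): 1 − 0.975^6 = 0.141.
- Adherence, physical health, readmissions and deaths (1A, 1B, 3, 4A, 4B): 1 − 0.975^5 = 0.119.

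**The case against.** The strongest reply is that this is a pilot. The protocol says so, and it asks for evidence of feasibility and acceptability. Neither document plans a claim of proven efficacy or makes a larger trial depend on a p-value. All 13 tests are listed in advance, so a reader can see the denominator. This stands as a limit on the consequence. It does not supply the missing label: the SAP states directional hypotheses that will be tested and nowhere calls them exploratory.

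A second reply is that the tests are not interchangeable. 2B and 2C sit under feasibility and acceptability, and 5A–5F under mechanisms. This also stands. A reader might infer that any one of the 13 could be offered as proof that Meds to Beds works, but the SAP's own grouping does not support that. The five tests on the effects named in the objective plus deaths carry 11.9% if independent, and less if correlated.

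A third reply concerns H1. Under an either-measure rule its favourable-direction error is at most about 4.9%, so the numerical inflation there is modest. That is correct. What remains is that the SAP leaves open which rule applies, and that choice could be made after the results are known.

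**Conclusion.** The concern holds at moderate size. The SAP sets 13 directional between-arm tests with no primary outcome, no error control, no exploratory label and no either/both rule for H1. Assuming two-sided 0.05 per test and no true effect, the chance of at least one favourable significant result is about 10–28% over correlations from 0.8 down to 0. One pre-named test would give 2.5%. The level, the sidedness and the correlations are assumptions, because the documents state none of them.

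A reader might infer a chance near one half. The documents do not support that as the headline. About 49% requires independent outcomes and either one-sided 5% testing, which the SAP does not specify, or counting results that go against the intervention, which cannot support any of these hypotheses. Likewise, 9.75% for H1 (1 − 0.95²) counts both directions under two-sided testing; the matching figure is 4.9%.

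A reader might also conclude that the plan needs a formal confirmatory family with a multiplicity procedure. For a pilot with no sample-size calculation, that goes further than the defect requires. Stating the status of each test is enough.

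**What to change.** Amend the SAP before any results are seen:

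1. State that H2A, delivery before discharge in at least 90%, is the pilot's feasibility criterion.
2. Name one adherence measure as the single lead efficacy outcome, tested at two-sided 0.05, with the other as supportive. Medication possession ratio (1A) is a reasonable choice, since it comes from pharmacy records rather than self-report. H1 then cannot be claimed on whichever measure is favourable.
3. Label 1B, 2B, 2C, 3, 4A, 4B and 5A–5F exploratory. Report the between-arm difference with a 95% confidence interval for every one of them, whatever the result, and do not describe any of these hypotheses as confirmed.

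The lead outcome then has a 2.5% chance of a false favourable result, and no claim of confirmation rests on the other 12. The cost is SAP wording only. The other outcomes lose confirmatory language. The lead outcome loses no power, because its test stays at the two-sided 0.05 assumed here.

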Participants will be identified and recruited from inpatient units at Jackson Memorial Hospital using the electronic health record. At consent, participants will be asked to sign a HIPAA waiver to allow access to their medical record for 60 days after discharge. 60 participants will be randomly assigned to one of two intervention conditions: 1) Meds to Beds, patients receive medication in-hand at discharge from the hospital, and 2) standard care (patient pickup at the pharmacy) comparison group. Adherence to medication will be measured with 1) self-report Adherence to Refills and Medications Scale (ARMS), and 2) pharmacy refill data. Health will be assessed with the self-report PROMIS 10, a measure developed by researchers for patient-reported evaluation of global health. Information on hospital readmission, other hospital visits, and deaths will be obtained from the electronic health record. Feasibility will be determined by tracking the number of patients who receive medications before discharge in the Meds to Beds intervention and by asking patients at follow-up how they received their discharge medications and about their experiences with healthcare. Acceptability will be assessed with 2 questions created for this study. A self-report questionnaire with 7 items created for this study will assess theoretical mechanisms of change for the Meds to Beds intervention. Self-report measures will be administered in-person before randomization, and/or about 30 days post-discharge by telephone or in-person. Prescription refill and other information from the electronic health record will be monitored for up to 60 days post-baseline in order to collect data about the period 30 days post-discharge. Measures are either available in English and Spanish from the authors, or will be translated using a translation back-translation approach.

6) Data and Specimen Banking*

There will be no specimen banking.

7) Data Management*

Protection of patient privacy and confidentiality will be maintained in highest priority at all times. All files will be kept in a locked office and data stored on a secured drive. All personally identifying patient information will be kept separate from patient data at all times.

8) Risks to Subjects*

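### Does the missing formula for Hypothesis 1A's 30-day medication possession ratio leave the direction of the result open?

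*SAP*

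**What the plan says.** Hypothesis 1 in the SAP is that "Participants in the intervention group will have better medication adherence than the control group". Its first part, H1A, reads: "Medication adherence (calculated with medication possession ratio) of participants in the intervention group will be higher" than in the control group at 30 days. The test is ANOVA.

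Protocol section 5 gives the data source: "Adherence to medication will be measured with 1) self-report Adherence to Refills and Medications Scale (ARMS), and 2) pharmacy refill data". It adds that records are followed for up to 60 days post-baseline, and gives the purpose as covering the 30 days after discharge.

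The intervention is described there as "Meds to Beds, patients receive medication in-hand at discharge from the hospital"; the comparison is patient pickup at the pharmacy. H2A expects that "The Meds to Beds intervention will have at least 90% successful deliveries of medication before discharge". H5A separately tests "The average length of time (in 0-30 days) before beginning a prescription medication regimen".

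Neither document states the ratio's numerator or denominator, a cap, the value for a patient with no fill, a rule for combining several drugs, or the handling of deaths and readmission days.

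**The concern.** In many trials the start date of a possession ratio is a neutral convention. Here it is not, because the intervention is the first fill. Whether a patient has a fill, and on what day, are effects of randomisation. A ratio from discharge in everyone randomised counts delay and non-filling. A ratio from first fill among fillers removes both and compares groups selected after randomisation.

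One patient shows the contrast. Take a single 14-day fill with no refill. Delivered on day 0, it scores 14/30 = 0.47 from either start. Picked up on day 20, it scores 10/30 = 0.33 from discharge but 10/10 = 1.00 from first fill.

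If the text left these choices equally open, two analysts could report different directions from the same records, and the definition could be picked after seeing the data. There is also a naming issue. If the first supply lasts 30 days or more, a discharge-based ratio shows only whether and when the first fill happened, which is narrower than adherence.

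**Working it through.** The plan states no power, alpha, effect size, SD or expected ratio, so there is no figure to reproduce.

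**Inputs from the documents.** 30 per arm (Protocol section 15); 90% delivered before discharge (H2A, a target); a 30-day window; ANOVA on two groups.

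**Assumed inputs.** Controls: 60% fill on day 0, 20% on day 3, 20% never. Intervention: 90% delivered on day 0, and the other 10% behave like controls. This gives 0.90 + 0.10 × 0.60 = 0.96 starting on day 0, 0.02 on day 3 and 0.02 never.

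**30-day supply, days covered, capped at 1**
- From discharge, no fill = 0. Control: 0.60 + 0.20 × 27/30 = 0.780. Intervention: 0.96 + 0.02 × 27/30 = 0.978. Difference +0.198.
- From discharge, fillers only: 0.978/0.98 - 0.780/0.80 = 0.998 - 0.975 = +0.023.
- From first fill, fillers only: 1.000 in both arms, difference 0.000.

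**30-day supply, days supplied over days elapsed, uncapped**
- From discharge, no fill = 0: 0.980 - 0.800 = +0.180.
- From discharge, fillers only: 1.000 - 1.000 = 0.000.
- From first fill to day 30, fillers only. A day-3 filler scores 30/27 = 1.11. Control: (0.60 + 0.20 × 30/27)/0.80 = 1.028. Intervention: (0.96 + 0.02 × 30/27)/0.98 = 1.002. Difference -0.026.

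**14-day supply, capped.** Usual fillers refill on time. Would-be non-fillers who receive a delivery do not refill.
- From discharge, no fill = 0. Control 0.780. Intervention: 0.90 × (0.80 + 0.20 × 14/30) + 0.10 × 0.780 = 0.882. Difference +0.102.
- From discharge, fillers only: 0.882/0.98 - 0.780/0.80 = 0.900 - 0.975 = -0.075.
- From first fill, fillers only. Control 1.000. Intervention: (0.72 + 0.18 × 14/30 + 0.08)/0.98 = 0.902. Difference -0.098.

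| Supply and ratio | Discharge, no fill = 0 | Discharge, fillers only | First fill, fillers only |
|---|---|---|---|
| 30 days, capped | +0.198 | +0.023 | 0.000 |
| 30 days, uncapped | +0.180 | 0.000 | -0.026 |
| 14 days, capped | +0.102 | -0.075 | -0.098 |

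**Chance of a significant result.** Simulation with 30 per arm, 4,000 runs, two-sided 0.05 (assumed), a 5-day delay, 20% late, 20% never filling, 85% refill among usual fillers, capped. With a 14-day supply, 25% of trials significantly favour Meds to Beds from discharge with no fill = 0, and 25% favour control from first fill among fillers. With a 30-day supply the figures are 83% for Meds to Beds and 0% for either arm. If delivered would-be non-fillers refill like everyone else (14-day supply), the three differences are +0.180, +0.032 and about 0, so nothing reverses.

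**Which column the text selects.**
- *Start.* H1A fixes the comparison at 30 days, and Protocol section 5 ties the records to the 30 days after discharge. Both indicate a window that opens at discharge. The longer record access serves that window and does not create a second one.
- *Patients with no fill.* H1A compares the intervention group with the control group, not fillers with fillers. With a discharge start, a patient with no fill has 0/30 = 0, an ordinary value. Only a first-fill start leaves it undefined.
- *Cap.* In the first column, a 30-day supply gives +0.198 capped and +0.180 uncapped: same direction, similar size.
- *Delay.* H5A gives time to start its own test, so H1A need not be rebuilt to isolate it.

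**The case for a change.** The strongest case for a change is that the start date alone does not settle the matter. With a discharge start kept, excluding patients with no fill moves the 14-day case from +0.102 to -0.075. The Protocol sentence about the 30 days after discharge describes data collection, not a denominator. Exclusion criterion 4 screens on the plan to use the hospital pharmacy, not on actual filling, so non-fillers can still occur. The SAP states a direction and a test, and one paragraph would close the gap cheaply.

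Much of this is true. The formula is absent, and that is not a redaction or a conversion fault. The two approaches do measure different things. But dropping randomised patients from a comparison of randomised groups would be an analyst's active departure, not something that the plan invites. The reversal also needs a first supply shorter than 30 days with delivered non-fillers who do not refill, or an uncapped ratio counted from first fill.

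The other open items (several drugs per patient, deaths, readmission days) would be applied alike in both arms. The documents give no rates from which to size them. A fill at another pharmacy could be scored 0 wrongly, mainly in the control arm. Criterion 4 limits this, and the Protocol already plans to check "by asking patients at follow-up how they received their discharge medications".

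Two cautions for the report stand. With a supply of 30 days or more, H1A shows possession over 30 days, and the self-report scale in H1B is the other adherence test. H5A's source is unstated; the Protocol says that "A self-report questionnaire with 7 items created for this study will assess theoretical mechanisms of change", but fill dates are also possible. If H5A uses the same fill dates, it is not separate support for H1A.

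**Conclusion.** The omission is real, but it is a gap that an analyst fills sensibly from the text: discharge to day 30, all randomised patients, no fill counted as 0. On that reading the assumed behaviour gives +0.102 to +0.198 in favour of Meds to Beds in the three cases tabulated, always in one direction. The contrary results (-0.026 to -0.098) appear only if fillers alone are analysed, and under conditions that the documents neither state nor suggest. With a 30-day supply capped at 1, the difference shrinks to 0.000 and never reverses.

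All shares, delays, supply lengths and refill rates are assumptions; only the 90% delivery target, 30 per arm, the 30-day window and the ANOVA come from the documents. This is a pilot that names no primary endpoint. The derivation used should be reported with the result, as for any possession ratio, but no amendment is needed.

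### Hypothesis 2 claims a high level of acceptability, but 2B and 2C test only whether Meds to Beds scores better than pharmacy pickup, and no level is set

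*SAP*

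**What the plan says.** The protocol (Objectives) expects this pilot to yield evidence on both feasibility and acceptability. SAP Hypothesis 2 turns that into a statement about a level: "The Meds to Bed intervention will have strong feasibility and acceptability".

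Three sub-hypotheses follow.

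- 2A is absolute: "The Meds to Beds intervention will have at least 90% successful deliveries of medication before discharge". Its analysis is confined to one arm: "Hypothesis 2A will be tested with a proportion in the intervention condition".
- 2B is comparative: "Participants in the Meds to Beds condition will report a better experience obtaining hospital discharge medications than those in the control group".
- 2C is comparative: "Participants in the Meds to Beds condition will report a better experience overall in the study than those in the control group".

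For the last two, the analysis is a between-arm test: "Hypotheses 2B and 2C will be tested using ANOVA".

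On measurement, the protocol (section 5, Procedures Involved) says "Acceptability will be assessed with 2 questions created for this study" and gives no wording, response scale or cut-off. The same section says that feasibility will be judged partly "by asking patients at follow-up how they received their discharge medications and about their experiences with healthcare". Neither document gives a target rating, an acceptability threshold or a planned summary of acceptability within the Meds to Beds arm.

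**The concern.** The word *strong* describes how the recipients of an intervention regard it. 2B and 2C ask a different question: whether one arm's mean rating exceeds the other's. The answer depends as much on how pharmacy pickup is received as on how Meds to Beds is received. An intervention that patients rate poorly can meet 2B or 2C if pickup is rated worse, and one that nearly everyone likes can miss both if pickup is also liked. The plan sets an absolute benchmark for the delivery half of Hypothesis 2 and none for the acceptability half.

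There is a second, smaller difficulty with 2C. As the SAP words it, the thing being rated is the participant's experience of the study. That would take in consent, interviews and the $20 and $50 compensation (protocol, section 14), which both arms have.

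Acceptability is one of the things this pilot is meant to establish. As written, the trial could report the wrong answer on it in either direction.

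**Working it through.** The documents give no alpha, SD, response scale, power calculation or acceptability threshold, so there is no planned figure to reproduce. What follows is illustration.

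**Inputs**

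- From the documents: 30 participants per arm (protocol, section 15), and ANOVA for 2B and 2C. With two groups this is the two-sample t-test.
- Assumed: two-sided alpha 0.05, complete data, a 1-5 rating with midpoint 3, and SD 0.8 in each arm for the first case.

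**1. A poor rating that passes**

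- Standard error of the difference = SD x sqrt(2/30) = 0.8 x 0.258 = 0.207.
- Means 2.6 v 2.0: t = 0.6 / 0.207 = 2.90 on 58 df, p = 0.005.
- Both means lie below the midpoint, yet the hypothesis is met.
- A simulation of 20,000 trials that does not rely on the SD assumption agrees. With an intervention mean of 2.53 (15% of patients giving a 4 or 5) against a control mean of 1.66 (5% giving a 4 or 5), the test is significant in the intervention's favour in 93.4% of trials.

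**2. A high rating that fails**

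- If the two arms have the same distribution, the chance of significance in the intervention's favour is 0.05 / 2 = 2.5%, however high the ratings are.
- Simulated with both means at 4.65 and 95% favourable in each arm: 2.3%.
- With 95% v 90% favourable (means 4.65 v 4.48): 15.6%.

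**3. The between-arm test in general**

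- The observed difference must exceed t(0.975, 58 df) x sqrt(2/30) = 2.002 x 0.258 = 0.52 SD to be significant.
- Power by the noncentral t is 11.5%, 20.7%, 47.8% and 86.1% at true standardised differences of 0.2, 0.3, 0.5 and 0.8. Reaching 80% needs about 0.74.

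**4. What a within-arm estimate would give at n = 30**

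| Favourable | Proportion | Exact (Clopper-Pearson) 95% interval |
|---|---|---|
| 24/30 | 80% | 61.4-92.3% |
| 27/30 | 90% | 73.5-97.9% |
| 29/30 | 97% | 82.8-99.9% |
| 30/30 | 100% | 88.4-100% |

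The choice between point estimate and lower limit matters. If the lower limit had to reach 90%, even 30/30 would fail. For illustrative values of 70% (unacceptable) and 90% (hoped for), neither of which is in the documents, requiring at least 26/30 has exact one-sided alpha 0.030 and power 0.82. Requiring at least 27/30, the smallest count whose lower limit exceeds 70%, has alpha 0.009 and power 0.65.

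**The case against.** Comparing arms is a proper question for a randomised pilot. Under 2B, control patients are not asked to rate something they never received; they rate their own experience of getting their medicines, and usual care is the natural yardstick. The first case above shows only that a difference test detects differences. All of this stands, and it is why 2B should be kept. It does not supply the level that Hypothesis 2 claims.

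The link from 2B and 2C to acceptability is inferred from the structure of Hypothesis 2 and from the protocol's two questions. Because the protocol lists questions on how medicines were received under feasibility, 2B could be a feasibility item. That also stands. On that reading, acceptability would rest on 2C alone, and the gap would be no smaller.

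Two stronger readings are tempting and should not be drawn.

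- *A satisfied control arm makes success impossible.* It does not. If every Meds to Beds patient scored 5 and the control SD were 0.8, the critical difference would be 2.002 x 0.8 / sqrt(30) = 0.29, so a control mean below about 4.71 could still be beaten. With less spread in the controls the limit is higher: all fives against 26 fives and 4 fours (mean 4.87) gives p = 0.04. Success is very unlikely when the arms are similarly satisfied, but there is no fixed ceiling.
- *2C measures the study and not the intervention, and is therefore biased.* The item is not reproduced, so only the SAP's summary wording can be judged. Study procedures common to both arms are balanced in expectation by randomisation. They may dilute the contrast, but they do not favour Meds to Beds.

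**Conclusion.** The point holds as a gap in the decision rule. The plan claims a level of acceptability but has no criterion for a level and no within-arm estimate, while its sister hypothesis 2A has both a benchmark and a single-arm proportion. The mismatch follows from the text alone. Its size is illustrative and rests on the assumed alpha, scale, SD and rating distributions: a rating of 2.6 out of 5 can pass at p = 0.005, and an intervention liked by 95% of its recipients has a chance of about 2.5% of passing if the controls are equally content.

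The criticism of 2C is conditional on the item matching the SAP's wording. The randomised comparisons themselves are not invalidated. This is a worthwhile and inexpensive correction to how one stated objective is judged.

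**What to change.** Amend the SAP under Hypothesis 2 as follows.

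- State which items measure acceptability.
- As the basis for the acceptability claim, specify the proportion of Meds to Beds participants who give a favourable rating on the existing item about getting discharge medicines, with an exact 95% interval. Define *favourable* on that item's actual response scale, and state the denominator.
- Fix the benchmark before any data review, and say whether the point estimate or the lower confidence limit must meet it.
- Keep 2B as a supportive between-arm comparison.
- Do not base the acceptability claim on 2C. It can still be reported.

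This needs no new patients, visits or data. No item needs rewording, which avoids revising the English and Spanish versions and avoids a break in comparability with anyone already assessed. The cost is SAP text and the sponsor's commitment to a threshold. Precision will be modest at n = 30, as the intervals above show, and lower with loss to follow-up: at an assumed 24 respondents, 20/24 (83%) gives 62.6-95.3%.
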